3.4.5. Genetic Assessments

The primary genetic assessment will include APOE genotype. Further genetic analysis will also be carried out in UoE. Current literature indicates that rare variants of strong genetic effect (APP, PSEN1&2) are too rare in the population to justify testing in the EPAD LCS. In addition, most of these rare mutations are observed in those with early onset AD and are unlikely therefore to be included in the EPAD LCS.

3.4.6. Other Measures

- *Date of birth – subject to local regulations*
- *Age*
- *Sex*
- *Ethnicity (Subject to local regulations) as categorized into one of following groups:*
 - Caucasian/white (includes people of Mediterranean, European, Hispanic, Middle Eastern origin)
 - Asian (includes people of Chinese, Indian, Pakistani, Bangladeshi, Japanese origin)
 - Black (includes people of African descent e.g. African American)
 - Combination of previous groups
 - Other

-
- *Education* as registered in number of years of formal education, as defined per country excluding short courses and internships in working/ learning program
 - *Handedness*
 - *Marital status*: married or cohabiting / widowed / divorced / single
 - *Family history of AD* in number of family members of first degree with history compatible with AD
 - *Body height* without shoes as recorded to the nearest cm
 - *Body weight* as measured to the nearest 0.1 kg without wearing shoes or heavy clothing. Body weight and height are used to calculate BMI
 - *Hip-waist circumference* as assessed to the nearest 0.1 cm
 - *Electrocardiogram (ECG)* will be recorded if any finding within the physical exam indicates its necessity. Data/findings and traces will be kept within the participant's study notes.
 - *Medical history* (yes/no):
 - Stroke
 - Diabetes (type 1 or 2)
 - Hypertension
 - Hypercholesterolemia
 - Myocardial infarction
 - Chronic ischemic heart disease
 - Chronic obstructive pulmonary disease
 - Asthma
 - Depression
 - Rheumatoid arthritis
 - Any cancer
 - General anaesthesia after the age of 50 years
 - Head injury assessed with the Brain Injury Screening Questionnaire (BISQ²⁹)
 - Mild Cognitive Impairment
 - Other conditions (listed as free text)
 - *Current medication*: name of drugs; treatment duration (<1year / 1-5years / >5years)
 - *Lifestyle factors*:
 - Smoking: never / past / current

-
- Alcohol consumption: units/week
 - Drug abuse/misuse: never / past / current; name of drug where applicable
 - Diet: Healthy Ageing through Internet Counselling in the Elderly (HATICE, www.hatice.eu) questionnaire
 - Physical activity, defined as leisure-time physical activity that lasts at least 20-30 minutes and causes breathlessness and sweating. Frequency will be assessed as: daily; 2-3 times a week; once a week; 2-3 times a month; a few times a year; or not at all³⁰
 - Life events: brief questionnaire based on the Swedish National study on Aging and Care (SNAC, <http://www.snac-k.se/>) questionnaire. SNAC questionnaires are not required to be completed if there are no change in reported events from the previous visit (e.g. at screening visit). Only changes (new events) from the previous visit should be reflected in the next completed SNAC questionnaire.
 - Self-rated health and self-rated fitness: Likert-type questions with response options very good / good / satisfactory / relatively poor / very poor³⁰
- *Dementia diagnosed by the participant's physician*: yes/no; type of dementia; date of diagnosis
 - *Mini-Mental Status Exam (MMSE)*. The MMSE is a 30-item mental status questionnaire that assesses a participant's mental status (orientation, memory, attention, language, visual-spatial abilities, and calculation). A total MMSE score is calculated by summing of all correct items out of a possible 30 points. The utility of MMSE, along with global indicators such as CDR, is principally as a clinical descriptor.³¹ MMSE was included in the standard clinical assessment as a standard measure that is regularly used in studies and recognized by regulatory authorities.
 - *Clinical Dementia Rating Scale (CDR)*. The CDR³² is comprised of two separate semi-structured face to face interviews one with the individual and another with a reliable collateral source (informant, i.e., partner, family member or relative, friend, or any other closely related individual) conducted by blinded independent, CDR certified Raters. Raters that conduct the CDR assessment on a particular research participant cannot rate any other assessments for that participant. During the interview, the clinician assesses the participant's current status in six domains (memory, orientation, judgment and problem solving, community affairs, home and hobbies, and personal care) and rated accordingly using a 5-point scale (0 = no impairment, 0.5 = questionable impairment, 1=mild dementia, 2 = moderate dementia, 3 = severe dementia, <http://knightadrc.wustl.edu/cdr/aboutcdr.htm>). Outcome measures of the CDR are a Global CDR score (derived from an algorithm developed by the The Charles F. and Joanne Knight Alzheimer's Disease Research Center [Knight ADRC]), the CDR sum of boxes (CDR-sb, the sum of all six domains), and a CDR rating for each domain. CDR raters, where possible, should be blinded, as far as possible, to all other cognitive and clinical assessments, except if biomarker status is disclosed. The rationale for the CDR rater remaining blinded is that if they know the status of the biomarker tests, or result of any other tests this could potentially influence how they score participants undertaking a CDR test.

-
- *Physical examination*, including e.g. neurological examination, blood pressure and pulse measurements.
 - *Depression*, The Geriatric Depression Scale (GDS)^{23,24} is a 30-item self-report assessment recorded by the clinician, used to identify depressive symptomatology in the elderly. The GDS questions are answered "yes" or "no". One point is assigned to each answer and the cumulative score is rated on a scoring grid. The grid sets a range of 0-9 as "normal", 10-19 as "mildly depressed", and 20-30 as "severely depressed". A diagnosis of clinical depression should not be based on GDS results alone. The test has well-established reliability and validity with 92% sensitivity and 89% specificity when evaluated against diagnostic criteria. Although a shorter version (15 items) has been validated, the longer version is more likely to have a normal distribution—hence better adapted for use as a dimensional scale—without reliance on theoretical clinical cut-off points. The larger range of items also permits a finer analysis by symptom cluster and not just overall score.
 - *Anxiety*, The State-Trait Anxiety Inventory (STAI)²⁵ is a psychological inventory based on a 4-point Likert Scale consisting of 40 self-report questions. The STAI measures separately both state anxiety (fear, nervousness, discomfort and autonomic nervous system arousal induced by specific situations) and trait anxiety (chronic feelings of stress, worry, discomfort experienced on a day-to-day basis). Each type of anxiety has its own scale of 20 different questions on a score range from 20 to 80, with higher scores correlating with greater anxiety.
 - *Sleep*, The Pittsburgh Sleep Quality Index²⁶ is a self-rated questionnaire that assesses sleep quality and disturbances over a one-month time interval. Nineteen items generate seven component scores: subjective sleep quality, sleep latency, sleep duration, habitual sleep efficiency, sleep disturbances, use of sleep medication, and sleep-related daytime dysfunction. The sum of scores for the seven components gives a global score. The index has adequate internal consistency and high retest reliability, with a diagnostic discriminability of 89.6% sensitivity and 86.5% specificity for good and poor sleepers.

Changes in depression, anxiety and sleep measures have been associated with both early biomarker change and cognitive dysfunction.

3.4.7. Biological Samples

- Blood samples will be collected at each annual visit
- Urine samples will be collected at each annual visit
- Saliva samples will be collected at each annual visit (refraining from caffeinated product prior to sampling; cortisol samples will not be collected for participants taking steroidal preparations e.g. oral, cream, ointment, inhaled or drops, these participants will be eligible to continue in the study and complete all other assessments including drool saliva collection)

Detailed instructions for the documentation, collection and management of the biological samples will be provided in a separate EPAD Sample Instruction Manual. Blood, urine and saliva samples will be collected annually in all EPAD LCS participants and CSF every 2 years for potential future

analyses of emerging AD biomarkers. Cortisol samples will be collected at baseline (Visit 1) and at 2 years (Visit 4) and then every second year. All biological samples will be stored at UoE, UK with reference to appropriate regulatory procedures.

3.4.8. 4-Monthly Telephone Contact

Participants will be contacted every 4 months throughout the duration of the study by telephone. However, if a 4-month call falls at the same time as a visit (i.e. months 12, 24, 36) this discussion will be done in person. This telephone call will serve as a reminder that participants are in a readiness cohort and may be invited to PoC trials in the future. Participants will be asked to indicate if they remain willing in principle to participate in these trials. Continued willingness to participate in PoC will be indicated in source data. If a participant responds that they are not willing to participate in the PoCs during a 4-month phone call, but had previously been willing in principle to participate when they were asked at baseline, as evidenced by a signed consent form, they will be eligible to remain in the LCS completing scheduled assessments and will continue to receive 4-monthly calls. Adverse events (AEs) related to study procedures from previous visits, changes to general health and medication use will also be checked during the 4 month phone call. There will be window of +/- 14 days surrounding the date of each 4 month phone call during which it can be performed. The 4-monthly point of contact should preferably be in the form a phone call, but if a participant prefers to be contacted by email then this is permitted as an alternative form of contact. Sites who contact their participants by email must do so as per their local email policy.

3.4.9. Visit Windows

The requirements of the protocol may necessitate the participant attending the clinic on more than one occasions to complete the requirements of each Visit. For Visit 1 all assessments should be completed within 28 days of the first assessment of the visit. For all following visits, all assessments should be completed within ± 21 days of the planned visit date based on the start of the study, i.e. tethered to the first assessment of Visit 1, except the MRI associated with the visit which should be completed within ± 42 days. This provides an 84-day window for each visit following Visit 1. Assessments that take place outside of these windows will be collected and included in the analysis but must be reported as a protocol deviation.

3.5. Study Completion or Withdrawal

The initial duration of EPAD LCS will be from April 2016 to June 2020, and extension of consent will be asked for prior to end of June 2020 assuming the EPAD LCS has funding to be maintained. Research participants will exit the EPAD LCS if:

- They withdraw consent at any time during the study
- They enter the EPAD PoC trial (after signing a separate ICF).
- They enter another clinical trial (continued participation in the parent cohort is expected)
- Safety reason or research participant not compliant with protocol procedures

-
- Sponsor's decision to stop the study
 - Decision by Balancing Committee to select/deselect individual participants. The Algorithm Running Committee will provide the output for the PCs.

For research participants selected for the EPAD PoC trial, the transition visit will become the last EPAD LCS visit. Research participants who complete the EPAD PoC trial, and still fulfil criteria for inclusion in EPAD LCS may return to EPAD LCS if they wish to at least 30 days after trial completion. Research participants who fail to meet the entry criteria for the EPAD PoC trial may return to EPAD LCS if they wish to at their next scheduled visit. The LCS visits for the returning research participants from PoC will be scheduled for the same time as their normal, annual LCS visit would have been due.

Any research participant who exits the EPAD LCS must be reported. Information about exiting EPAD LCS, date and reason (if given by the research participant) will be recorded. Also for these research participants, the investigator must complete the Case Report Form (CRF) including the clinical summary.

Alternative medical care for research participants exiting EPAD LCS is to be arranged by the TDC investigator if necessary. For those research participants who discontinued due to the occurrence of AEs potentially related to study procedures, follow-up must be reported until the AE has abated, or until a stable situation has been reached, with findings being recorded in the eCRF.

3.5.1. Participant Re-Screening

If a participant screen fails for a reason that the Investigator deems resolvable then it is possible to rescreen the participant at a later date, with prior approval from the Chief Investigator. In the event of a re-screen the participant should be given a new study identification number and it should be clearly marked within the study data that the participant previously screen failed. If the participant screen fails on a second occasion, then there should be no attempt to include them further in the study. It should be under the investigators guidance and best interests of the participant if any action is taken to re-screen for the study (i.e. withdrawal from an active CTIMP to re-screen).

3.5.2. Lost to Follow up

An individual may be considered as lost to follow up when the TDC has conducted 3 follow up attempts to schedule a study visit with any participant that is not responsive. All attempts should be documented in source documentation at the TDC which should include the date, time and outcome.

4. STATISTICAL ANALYSIS METHODS

4.1. Determination of Sample Size

A constant sample size of approximately 3,500 research participants for the EPAD-LCS is considered sufficient for a readiness cohort that should provide approx. 1,500 research participants for the EPAD PoC trial. The EPAD-LCS sample size will be maintained constant through continuous recruitment from the PCs. Involvement of multiple PCs connected to EPAD Consortium members or outside EPAD will ensure that the PCs continue to provide the necessary number of research participants over time.

The estimated number of research participants to be entered in EPAD LCS from 2016 until end of June 2020 is 3,500.

Strategies for motivation and engagement, as well as improving the research experience for participants will be developed in EPAD LCS, including proven techniques like newsletters, websites and telephone contact from the TDCs. There is a selection bias from PCs as it is likely that it will be those research participants who are most motivated who will agree to join the EPAD LCS with a clear intent of entering the EPAD PoC trial.

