The flow of research participants from the population at large to the trial is divided into the following stages: firstly, EPAD will engage existing PCs from across Europe who may have eligible research participants for the EPAD LCS. The next step is drawing research participants from the PCs into the EPAD LCS to maintain a suitable population of approximately 3,500 research participants. This main form of recruitment for the EPAD LCS is complemented with research participants who come from a clinical setting, they or their referring clinician will contact EPAD LCS centres directly. Finally, research participants in the EPAD LCS who fulfil trial inclusion criteria (approximately 1,500 research participants), will be invited to enter the EPAD PoC trial for evaluation of treatment for secondary prevention of AD dementia. This trial is a standing, adaptive, PoC trial that could involve multiple arms running concurrently. Successful graduation through PoC into phase 3 confirmatory trials of single or combinatorial interventions will be based on success against an intermediary, target specific biomarker and then success against a cognitive measure.

Once recruitment is completed, at any given time there should be approx. 3,500 research participants in the EPAD LCS and approximately 1,500 in the EPAD PoC, hence the need to replenish each from PCs as participants are lost through attrition. EPAD LCS will initially run until the end of June 2020, and extension of consent will be sought prior to this date.

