3. RESEARCH METHODS

3.1. Study Design and Rationale

EPAD LCS is a prospective, multicentre, Pan-European, cohort study that will have a well-phenotyped probability-spectrum population to address the dual need to develop accurate longitudinal models for AD covering the entire disease course, and to create a pool of highly characterized individuals for the EPAD PoC trial. EPAD LCS participants will be recruited from different types of existing PCs across Europe (e.g. memory clinic-based, population-based) to ensure fast recruitment of a probability-spectrum population covering the entire continuum of probability for AD dementia development.

The study design is summarised in Figure 1.

¹ Once recruitment is completed, at any given time there should be approx. 3,500 research participants in the EPAD LCS and approx. 1,500 in the EPAD PoC, hence the need to replenish each as participants are lost through attrition.

Figure 1: Research participants flow to the EPAD LCS and into the EPAD PoC trial

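### Section 4.1 uses 3,500 both as the constant standing LCS and as total entries to June 2020; 3,500 in the LCS with 1,500 in the PoC needs at least 5,000 entries

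*Protocol*

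**What the plan says.** Section 4.1 opens with a standing size: "A constant sample size of approximately 3,500 research participants for the EPAD-LCS is considered sufficient for a readiness cohort". It adds that this cohort "should provide approx. 1,500 research participants for the EPAD PoC trial", and says how the size is to be held: "The EPAD-LCS sample size will be maintained constant through continuous recruitment from the PCs". The next paragraph gives a cumulative count for the initial study period: "The estimated number of research participants to be entered in EPAD LCS from 2016 until end of June 2020 is 3,500".

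Section 1.2 makes the two cohorts concurrent: "at any given time there should be approx. 3,500 research participants in the EPAD LCS and approximately 1,500 in the EPAD PoC". The footnote to Figure 1 in section 3.1 says the same ("at any given time there should be approx. 3,500 research participants in the EPAD LCS and approx. 1,500 in the EPAD PoC"), and the synopsis carries an identical footnote. In each place the sentence is conditional on recruitment having been completed. Section 3.3 repeats the standing 3,500 under that condition and says the cohort is refilled continuously from the parent cohorts.

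Section 1.2 also says where the PoC participants come from: "research participants in the EPAD LCS who fulfil trial inclusion criteria (approximately 1,500 research participants), will be invited to enter the EPAD PoC trial". Section 3.5 lists PoC entry among the reasons for leaving the LCS and makes the transition visit the last LCS visit. Under sections 3.3 and 3.5, people who complete the PoC may return at least 30 days later if they wish and are still eligible, and those who fail PoC entry criteria may return at their next scheduled visit. No attrition rate, return rate or replacement count is given.

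**The concern.** A cumulative count of entrants equals a standing count only if nobody is away. This protocol expects people to leave: by withdrawal, by entering another trial, by deselection and, by design, by moving to the PoC. Using 3,500 for both quantities in one section leaves no room for any of these exits, although the same section relies on continuous refilling.

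Section 4.1 contains no power or precision calculation, so these head-counts are the whole justification of size. The readiness claim (objective 1) and the recruitment target for parent cohorts and sites depend on them. A site or funder reading section 4.1 cannot tell whether to plan for 3,500 entries or for more than 5,000, or whether the pool under LCS follow-up is meant to be 3,500 or about 2,000 while the PoC is full.

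**Working it through.** **Inputs from the protocol**
- Cumulative entries to end of June 2020: E = 3,500 (4.1).
- Standing LCS: L = 3,500 (4.1, 1.2, 3.3, footnotes).
- In the PoC at the same time: P = 1,500 (1.2, footnotes).
- PoC participants are drawn from the LCS (1.2) and leave it on entry (3.5), so nobody is counted in both.

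**Balance.** At any moment, E = (in LCS) + (in PoC) + (other losses).

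**The plan's own figure.** E = 3,500 agrees with L = 3,500 only if the PoC count and all other losses are zero. With P = 1,500 it is not reproduced.

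**Entries needed for the concurrent state, no attrition**
- L + P = 3,500 + 1,500 = 5,000.
- Shortfall: 5,000 - 3,500 = 1,500. Ratio: 5,000 / 3,500 = 1.43.

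**LCS available from 3,500 entries, no attrition**
- E - P = 3,500 - 1,500 = 2,000, and 2,000 / 3,500 = 57%.

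**Effect of returners.** Suppose instead that 1,500 is a cumulative number of transfers, a share r has returned to the LCS, and there are no other losses. The LCS is then 2,000 + 1,500r and the PoC or other absence is 1,500(1 - r).

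| r | LCS | Not in LCS |
|---|---|---|
| 0% | 2,000 | 1,500 |
| 25% | 2,375 | 1,125 |
| 50% | 2,750 | 750 |
| 75% | 3,125 | 375 |

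Each row sums to 3,500. Returners raise the LCS only by lowering the number in the PoC, so no row reaches the 5,000 that the concurrent statement needs.

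**Illustration with attrition (assumptions, not protocol figures).** Take even entry over April 2016 to June 2020 (51 months, T = 4.25 years) and a constant exit rate a per year, applied to all entrants. The fraction still enrolled at the end is f = (1 - exp(-aT)) / (aT).

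| a per year | f | LCS left: 3,500f - 1,500 | Entries needed: 5,000 / f |
|---|---|---|---|
| 5% | 0.901 | 1,653 | 5,550 |
| 10% | 0.815 | 1,351 | 6,138 |
| 15% | 0.739 | 1,088 | 6,762 |

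The 5,000 and the 2,000 need no outside figure. The second table depends wholly on the assumed rates and even entry.

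**The case against.** The strongest defence is timing. The 3,500 plus 1,500 is promised only once recruitment is complete, June 2020 ends only the initial period, and an extension is foreseen. On that reading, 3,500 entries are the initial fill and the concurrent state comes later. Nothing in the protocol dates the 1,500, and section 4.1 does not say that they are in the PoC simultaneously.

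This stands in part. A reader might infer that the LCS will hold only 2,000 by June 2020, or that the design as written delivers well under 60% of its cohort. The documents do not support either. The 57% is a ceiling that applies when 1,500 are in the PoC at once, and anything lower rests on attrition and entry patterns that the protocol does not state.

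The initial-fill reading still does not reconcile section 4.1. With 3,500 entered, having 3,500 present requires that nobody is away. Section 3.5 lists several routes out, and the synopsis (follow-up) lets eligible prodromal and preclinical participants leave for the PoC straight after baseline. If no transfers were expected before June 2020, section 4.1 does not say so. The words for approximation and estimation cannot absorb a gap of 1,500.

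A reader might also infer that the data for disease modelling shrink to 2,000 people. That does not follow. Section 6.2 keeps data collected before withdrawal usable, run-in data from people who go on to the PoC are an objective in section 2, and the longitudinal models of section 4.3 can use everyone who contributed data.

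It is also fair that the study is observational, that its size is not power-based, and that no test or error rate depends on these figures. I could read only the Figure 1 footnote, so any counts inside the figure are unchecked.

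**Conclusion.** The inconsistency is real and sits within one short section. The concurrent 3,500 and 1,500 require at least 5,000 cumulative entries, 1.43 times the number stated. With 3,500 entries, the LCS is at most about 2,000 whenever 1,500 are in the PoC together, and below 3,500 after any exit that is not offset by a return. This rests only on the protocol's head-counts and on its rule that PoC entrants leave the LCS. The attrition figures are illustrative. What is affected is the stated size, the readiness claim and the recruitment target. The number of people informing the disease models is not.

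**What to change.** In sections 4.1, 1.2 and 3.3, the Figure 1 footnote and the identical synopsis footnote, separate cumulative entries from standing size. Give one consistent set of figures with the assumed number and timing of PoC transfers, the share returning, and the attrition rate. The sponsor has to choose which meaning of 3,500 is intended:

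- **3,500 is cumulative entry to June 2020.** Restate the standing LCS as 3,500 less those in the PoC and other exits, which is at most about 2,000 with 1,500 in the PoC, and base the readiness statement on that.
- **3,500 plus 1,500 is the target.** Label it as a later steady state and state the cumulative entries it implies: 5,000 plus replacement at the assumed attrition rate.

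In either case, leave the modelling sample defined by all entrants with data.

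The cost is wording in five places. The first option needs no extra enrolment, but a stated figure becomes less favourable and the promise of a constant 3,500 has to be given up. The second makes explicit at least 1,500 entries beyond the 3,500 now stated, which the standing-cohort promise already implies.
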